9.36 Population PK Evaluations

Blood samples for estimation of population PK characteristics of ETR will be collected at study weeks 4, 8, 12, 24 and 48, and at the determination of virologic failure, as outlined in the schedule of evaluations (Appendix I). At Weeks 4 and 24, one sample should be timed to fall within a window of 1 to 4 hours following a dose of ETR; at week 8, one sample should be timed to fall within a window of 4 to 8 hours following a dose of ETR; and at weeks 12 and 48, one sample should be timed to fall within a window of 8 to 12 hours following a dose of ETR. ETR plasma concentrations will be determined in a CLIA-certified IMPAACT Pharmacology Laboratory (refer to LPC).

9.4 Population Pharmacokinetic Study Design, Modeling and Data Analysis

For this analysis, the primary interest will be the PK characteristics of ETR and these will be evaluated using NONMEM version VII (GloboMax, Hanover, MD). NONMEM uses mixed effects (random and fixed) regression to estimate population means and variances of PK parameters and to identify intrinsic and extrinsic factors, such as body weight, sex or concomitant drug that may influence these parameters. Base models will be developed using first-order conditional estimation with or without interaction. A stepwise procedure will be used to determine whether a one- or two-compartment model best fits the plasma data under the principle of parsimony. A log-normal error distribution will be assumed for the description of both interpatient and intrapatient (residual) PK parameter variability. If necessary, poorly identified structural parameters, such as the absorption rate constant, may be fixed. The following covariates will be collected at baseline or during follow-up visits: sex, age, weight, race, HIV regimen (e.g., boosted PI) and HIV response markers. The influence of each covariate on the PK characteristics of ETR will be tested sequentially. At each step, the goodness of fit plots will also be evaluated. At the end of the analysis, all

covariates that show an influence on the parameters will be evaluated again by comparison of the full model (with all factors included) with a model from which each of the factors is deleted sequentially. For forward addition and backward elimination a decrease in objective function value by 3.84 ($p \leq 0.05$) and 6.64 ($p \leq 0.01$), respectively, would advocate sufficiently influential covariates. P1090 data may be supplemented with other pediatric PK data from previous etravirine studies (TMC125-C213, TMC125-C126) to support structural model and/or parameter precision if needed.

NONMEM uses extended least squares to calculate the objective function and the difference in the value of the objective function between models is approximately chi squared distributed. A difference in objective function of greater than 6.6 is considered significant (6.6 corresponds to a chi square for $p = 0.01$ with 1 degree of freedom) when one parameter is added or the covariate (e.g., body weight) is replaced. This is analogous to the commonly used F test to select among regression models. The primary outcome of this analysis is to identify the model that best describes the plasma PK of ETR and to investigate whether any of the covariates influences the PK of ETR. The final model will include all significant covariates (if any) and the parameter estimates for all parameters together with the estimates of residual and inter-individual variability. A secondary objective of this combined analysis will be to develop a linked population PKPD model in NONMEM to evaluate potential relationships between these plasma concentrations/PK characteristics and therapeutic outcomes (i.e. response to HIV therapy after 48 weeks of ETR and adverse events).

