2.2 Secondary Objectives

- 2.21 To assess the antiretroviral activity of ETR containing regimens through 48 weeks of therapy.
- 2.22 To determine the immunological changes (change in CD4 percent and absolute count; CD4/CD8 ratio and percent) through 48 weeks of ETR therapy in combination with an OBR.
- 2.23 To determine changes in viral drug resistance during 48 weeks of ETR therapy in combination with an OBR.
- 2.24 To assess the relationship between ETR pharmacokinetics and the antiviral activity and safety of ETR containing regimens.
- 2.25 To explore the relationship between subject-specific gene CYP profile, sex, age, weight, race, HIV regimen (e.g., boosted PI) and HIV response markers and pharmacokinetics of ETR.

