Correlations between baseline HIV genotypic and phenotypic drug resistance and any subsequent virologic failure will be evaluated. Subjects will be assessed for HIV genotypic and phenotypic drug resistance to the OBT and ETR at screening, at the time of virologic failure (if this occurs) and at early discontinuation.

8.6324 Additional Interim Analyses for Regulatory Purposes

To comply with regulatory requirements, additional interim analyses of data from Cohort 1 will be performed when at least 12 evaluable subjects have reached Week 24 and Week 48. Also to address regulatory expectations, an additional analysis across all age cohorts will be performed through Week 48 on at least 18 subjects. These analyses will be performed by Janssen R&D and will focus primarily on safety data, presented as described in Section 8.631 and pharmacokinetic data, presented as described in Section 9.0. A secondary analysis of virologic success, as described in Section 8.6321 will also be presented. These analyses will be shared with the P1090 Team.

8.633 Exploratory Analyses

8.6331 CYP Gene Profiles

Descriptive analyses will examine the association between pharmacokinetic parameters of ETR and subject-specific CYP gene profiles.

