9.2 Primary and Secondary Data

Primary: AUC_{12h}

Secondary: C_{max} , C_{12hr} , T_{max} , CL/F , $T_{1/2}$, Vd and PK parameters (C_{max} and C_{12hr}) by CYP2C9 and CYP2C19 genotype

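### CYP genotype is part of secondary objective 2.25 and is sampled at entry, but no covariate-adjusted effect of genotype on etravirine clearance is prespecified

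*Protocol*

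**What the plan says.** Protocol Section 2.2, objective 2.25, is a secondary objective: "To explore the relationship between subject-specific gene CYP profile, sex, age, weight, race, HIV regimen", together with HIV response markers, and etravirine pharmacokinetics. SAP Section 4 repeats it.

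CYP genotyping is marked at Entry in Appendices IA, IB and IC. For Cohort III, footnote 11 of Appendix IC allows the blood for genotyping to be skipped in the youngest infants if the volume is hard to draw.

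The analysis is spread over four places:

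- **Protocol 9.4 (population PK):** "The following covariates will be collected at baseline or during follow-up visits: sex, age, weight, race, HIV regimen (e.g., boosted PI) and HIV response markers". It continues: "The influence of each covariate on the PK characteristics of ETR will be tested sequentially".
- **Protocol 9.2:** the secondary data include Cmax and C12h "by CYP2C9 and CYP2C19 genotype". AUC12h (the primary parameter) and CL/F appear in 9.2, but not as by-genotype comparisons.
- **Protocol 8.6331, under exploratory analyses:** "Descriptive analyses will examine the association between pharmacokinetic parameters of ETR and subject-specific CYP gene profiles".
- **SAP:** CYP profile is an exploratory response variable in Section 5. Section 6 contains no CYP analysis, and Section 6.3 leaves pharmacokinetics to the protocol pharmacologist.

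Section 9.4 also gives two rules for adding a covariate. Its first paragraph uses an objective-function drop of 3.84 for forward addition and 6.64 for backward elimination. Its second says, for one added parameter or a replaced covariate: "A difference in objective function of greater than 6.6 is considered significant".

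**The concern.** A genotype of a metabolising enzyme acts on clearance. The model that estimates clearance while accounting for weight, age and companion drugs is the one in 9.4, and genotype is not among its covariates. The only by-genotype comparison that names its parameters, in 9.2, uses observed concentrations. These move with the dose given and with the child's size, so a difference between genotype groups could reflect who was in which weight band, and a real difference could be hidden in the same way.

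Section 9.34 adds to this. Doses of children with low AUC12h are prorated towards a common exposure, so concentrations taken after adjustment would tend to shrink a genotype difference. Section 9.2 does not say which visit is compared.

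At stake is how well a stated secondary objective is answered with a sample the children already give. Dose selection does not depend on it.

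**Working it through.** **1. Objective against covariate list**

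| Factor | Objective 2.25 | 9.4 covariates | 9.2 by genotype | 8.6331 |
|---|---|---|---|---|
| CYP profile | yes | no | Cmax, C12h | PK parameters, unrestricted, descriptive |
| Sex, age, weight, race | yes | yes | – | – |
| HIV regimen (e.g. boosted PI) | yes | yes | – | – |
| HIV response markers | yes | yes | – | – |

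The 9.4 list is the list in 2.25, in the same order, without CYP. It is not marked as examples, and the covariates it lists are the ones tested. Section 9.33 calculates CL/F as dose/AUC12h from the intensive PK visit, so the parameter needed exists.

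**2. How far dose and size move the parameters (Appendix III)**

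- Table 2, just under 8 kg: 37.5/8 = 4.7 mg/kg. Table 1, 10 kg: 100/10 = 10 mg/kg. Ratio 10/4.7 = 2.1. (Just under 6 kg, Table 2 gives 25/6 = 4.2 mg/kg.)
- With the clearance exponent of 0.75 in Section 1.32: 37.5/8^0.75 = 7.9 and 100/10^0.75 = 17.8. Ratio 2.3.
- Within Table 1, 10 kg and just under 20 kg both receive 100 mg: (20/10)^0.75 = 1.7.

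The last line also applies to CL/F. Under the same exponent, a child of nearly 20 kg has about 1.7 times the CL/F of a child of 10 kg. A descriptive split of CL/F by genotype removes the dose term but not weight, which is why the adjusted model matters. Section 9.34 also says that etravirine PK is not dose-proportional, so CL/F removes dose only approximately.

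**3. Thresholds**

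Chi-square, 1 df: 3.84 gives p = 0.0500, 6.64 gives p = 0.00997 and 6.6 gives p = 0.0102. The stated p-values are reproduced. For a three-level genotype (2 df), the 0.05 and 0.01 points are 5.99 and 9.21.

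A drop between 3.84 and 6.6 enters a covariate under the first paragraph of 9.4 and not under the second. To be kept, it must still pass 6.64 in backward elimination.

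**4. What 36 children could show**

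The documents give no genotype frequency, so a share of 10% to 50% is assumed. Detectable CL/F ratio, two groups, two-sided 0.05, 80% power:

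exp[(1.960 + 0.842) × s × √(1/n1 + 1/n2)], with s = √ln(1 + CV²).

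| AUC12h source (Section 1.32) | CV | s | share 10% (3.6 v 32.4) | share 50% (18 v 18) |
|---|---|---|---|---|
| Adults, DUET | 4710/5506 = 0.855 | 0.741 | 3.2 | 2.0 |
| PIANO, 6 to <12 years | 2845/5260 = 0.541 | 0.507 | 2.2 | 1.6 |

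This takes the spread of log AUC12h as that of log CL/F, without adjustment for weight or regimen.

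**The case against.** The strongest reply is that the plan covers this already. Section 8.6331 is not limited to two parameters, CL/F is calculated, and a descriptive association suits an objective worded as exploration. That much stands. A reader who stops at 9.2 might infer that genotype is compared only on Cmax and C12h, that its effect on clearance is never estimated, or that objective 2.25 cannot be answered. The documents do not support any of these. With PK left to the pharmacologist in SAP 6.3, they also cannot show what a separate PK plan contains. What the reply does not supply is an adjusted estimate, or agreement in scope between 9.2 and 8.6331.

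Three further inferences go too far:

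- **That dose alone could produce a two-fold genotype difference.** This would need genotype to line up with opposite extremes of the dosing tables, and nothing in the documents links them. The weight bands were also chosen by simulation to give similar exposures. The realistic effect is added noise and chance imbalance.
- **That omitting genotype undermines the age comparison.** Section 1.32 concerns enzyme maturation, not inherited genotype, and age is already a tested covariate. Genotype could at most explain some of the remaining variability, of unknown size.
- **That the two thresholds give different final models as a rule.** A covariate whose drop stays between 3.84 and 6.6 is not retained under either. Mostly the selection path differs.

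A careless remedy could also do harm. A category for missing genotype would fall mainly in the youngest infants and could absorb part of the age effect. Raw AUC12h by genotype would be as dose-dependent as Cmax.

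**Conclusion.** The gap is real and narrow. CYP genotype belongs to a secondary objective and is scheduled for collection, yet no CYP effect on CL/F adjusted for weight, age and boosted PI is prespecified. This rests on reading the 9.4 list as complete, which is how it is written.

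The weight is modest. The CYP analysis is labelled exploratory, and on the assumptions above only a CL/F ratio of about 1.6 to 3.2 would be detected. Missing infant genotypes would push that higher. The case for changing the plan is that a planned model and a scheduled sample can answer the objective better at almost no cost, not that any primary conclusion is at risk. The threshold discrepancy is a separate, small inconsistency that applies to every one-parameter covariate.

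**What to change.** 1. **Section 9.4:** add CYP2C9 and CYP2C19 genotype to the covariates tested on CL/F, after weight and age are in the model and with boosted PI among the covariates. State the coding in advance and match the thresholds to it: 3.84 forward and 6.64 backward for 1 df, 5.99 and 9.21 for 2 df.
2. **Missing genotype:** fit in genotyped children, or use a mixture or imputation approach. Do not use a category for missing genotype. Report the age effect with and without genotype, in the same children, so that a change is not caused by a change of sample.
3. **Section 9.2:** add CL/F to the by-genotype summary so that it matches 8.6331. Dose-normalised AUC12h (AUC12h/dose, the reciprocal of CL/F) may be shown beside it. State that values come from the intensive PK visit on the starting dose.
4. **Section 9.4 thresholds:** keep one forward-addition rule and remove the other, noting that retention needs a drop of about 6.6 either way for 1 df.
5. **SAP 6.3:** point to the document that holds the CYP analysis.

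The cost is a few sentences, one or two extra model parameters per gene and one or two table rows, with no new blood or visits. The downside is imprecision: with about 36 children and some infants not genotyped, the estimate will have a wide interval and should be reported as exploratory.

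### Section 9.4 allows follow-up HIV response markers into the population PK model that then supplies the exposure for the PK–response analysis, so the antiviral part of objective 2.24 can become circular

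*Protocol*

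**What the plan says.** Protocol Section 9.4 describes one combined NONMEM analysis.

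- **Candidates.** The covariates are those "collected at baseline or during follow-up visits: sex, age, weight, race, HIV regimen (e.g., boosted PI) and HIV response markers". The timing phrase covers the whole list; no item has its own time point.
- **Direction.** "The influence of each covariate on the PK characteristics of ETR will be tested sequentially". Each item is thus a predictor of PK.
- **Retention.** Forward entry needs a drop of 3.84 in the objective function and backward retention needs 6.64. A later paragraph of the same section says "A difference in objective function of greater than 6.6 is considered significant" when one parameter is added. All covariates found significant, if there are any, go into the final model.
- **Next use.** "A secondary objective of this combined analysis will be to develop a linked population PKPD model in NONMEM", in order to "evaluate potential relationships between these plasma concentrations/PK characteristics and therapeutic outcomes". The outcomes named are response to HIV therapy after 48 weeks and adverse events.

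This step serves objective 2.24: "To assess the relationship between ETR pharmacokinetics and the antiviral activity and safety of ETR containing regimens". Objective 2.25 separately explores HIV response markers and PK together, without a direction. SAP Section 6.3 adds no PK method; it leaves PK to the protocol pharmacologist.

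**The concern.** HIV response comes after exposure and adherence; it does not cause clearance. A child who misses doses has low sparse concentrations, which a model without adherence reads as high apparent CL/F, and the same child tends to respond poorly. A follow-up marker can therefore be picked up as a covariate on CL/F. Each child's estimated exposure would then contain part of the outcome it is next used to explain.

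The route is plausible in this trial. Protocol Section 9.33 requires seven days without a missed dose before the intensive PK visit, but Section 9.36 sets no such condition for the sparse samples and adds a sample at virologic failure. Section 6.6 says adherence problems are frequent in children and provides for adherence data, yet adherence is not on the Section 9.4 covariate list.

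At stake are the antiviral half of objective 2.24 and the pharmacodynamic outcome anticipated in Section 9.5. The adverse-event half is less directly exposed.

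**Working it through.** **1. The plan's thresholds.** The chi-square upper tail on 1 df gives 0.0500 for 3.84, 0.0100 for 6.64 and 0.0102 for 6.6. The stated p-values reproduce. The entry rule for an added covariate is not consistent, however: 3.84 in one paragraph and more than 6.6 in the next.

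**2. How strong a marker must be to stay.** In a linear Gaussian approximation the drop in objective function is −N·ln(1−r²), where r is the correlation between the marker and log CL/F. Retention at 6.64 needs |r| > √(1−exp(−6.64/N)).
- N = 36 (the planned evaluable number): √(1−exp(−0.1844)) = √0.168 = 0.41.
- N = 40 (used in step 3): √(1−exp(−0.166)) = √0.153 = 0.39.

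**3. How often a marker stays.**

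*No adherence confounding.* One unrelated marker was retained in 1.1% to 1.4% of 20,000 simulated trials (N = 36 and 50). For k independent unrelated markers the chance that at least one passes is 1−0.99^k: 3.0% for 3, 4.9% for 5, 9.6% for 10. The documents do not give k.

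*With adherence confounding.* Assumptions: N = 40; poor adherers have 2 to 3 times higher apparent CL/F; 25% of them respond, against 75% of the others; response has no effect on clearance. The documents give a guide to variability. The PIANO AUC12h of 4820 (SD 4157) in Protocol Table 3 has CV 4157/4820 = 0.862, so log-SD = √ln(1+0.862²) = 0.75.

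| Between-child log-SD of CL/F | 20% poor adherers | 30% poor adherers |
|---|---|---|
| 0.5 | 11–24% | 18–36% |
| 0.75 | 6–13% | 9–20% |

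The table ignores estimation error. With log-SD 0.6 to 0.75 and estimation error equivalent to 10–50% shrinkage, retention is roughly 3% to 26% across both proportions of poor adherers. It falls further if the intensive samples dominate. Of the 12 scheduled samples per child, 7 are intensive and 5 sparse. Scaling the log fold change by 5/12 (an assumption) gives about 2–4% with 20% poor adherers.

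**4. What a retained marker does.** Take the marker to be the outcome itself. A child's estimate is the fitted marker effect plus w times that child's residual, where w is the weight on the child's own data. Without the marker, shrinkage rescales every estimate alike and leaves r unchanged. With it,

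r′ = r / √(r² + w²(1−r²)).

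- With w = 1−s for shrinkage s, and r = 0.46 (the mean among retained cases at N = 36): s = 10% gives 0.50; s = 30% gives 0.46/√(0.2116+0.49×0.7884) = 0.59; s = 60% gives 0.46/√(0.2116+0.16×0.7884) = 0.79. The simulated means agree.
- If between-child variance is re-estimated once the marker is in, w = (1−r²−s)/(1−r²). With r = 0.45, w is 0.875, 0.624 and 0.373 at s = 10%, 30% and 50%, and r′ is 0.50, 0.63 and 0.80. Simulated means at N = 40 were about 0.5, 0.64 and 0.81.

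**5. Effect on false positives.** With no adherence confounding, type I error of the exposure–response test moved only from 0.047–0.053 to 0.049–0.058, because a marker is so rarely kept. If a marker were forced in whatever its significance (not the plan's rule), it would be 0.11 to 0.17 at 30% shrinkage and 0.42 at 60% (N = 36).

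**The case against.** The best defence is that Section 9.4 permits the problem but does not prescribe it. The covariate list mixes fixed and changing items, and baseline RNA and CD4 may be all that is meant. Retention is conditional. The exposure metric for the response step is not fixed, and Section 9.33 provides a non-compartmental AUC12h that owes nothing to the covariate model. PK detail may also sit in the pharmacologist's plan, which is not among the documents. All of this stands, and it is why the point is that the analysis can become circular. A reader might infer that it is circular as written; the text does not support that.

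A second objection also stands. The retention test is symmetric, so the frequencies in step 3 measure adherence confounding, and the underlying correlation of about 0.45 remains if the marker is deleted. Only the rise from there to 0.5–0.8 belongs to the circularity. For the same reason, the CL/F difference between responders and non-responders in trials where the marker was kept is inflated by selection and should not be quoted as a bias.

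A reader might also infer that dose selection is compromised. It is not shown to be. Sections 9.31, 9.34 and 9.35 judge dose on AUC12h from the intensive visit, Section 1.32 describes the dose-simulation model with body weight as its covariate, and no section says that the final Section 9.4 model supplies clearance for dosing.

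Objective 2.25 does name response markers, but without direction, so it does not require follow-up response as a predictor of PK.

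**Conclusion.** The concern holds as a conditional one. The written rules allow follow-up response to predict PK, keep it if significant, and then use that PK to explain 48-week response, with no safeguard in the protocol or SAP. Two conditions must both be met for harm: a follow-up marker is retained, and covariate-informed estimates are the exposure.

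The first is uncommon to moderately likely: about 1% with no adherence confounding, and roughly 3% to 26% with 20–30% poor adherers. These figures rest on assumed variability, fold change, response rates and shrinkage. When both conditions are met, the exposure–response correlation is inflated, slightly at 10% shrinkage and heavily at 50–60%. The damage is mainly to the apparent strength of the relation; the overall false-positive rate barely moves in the unconfounded case. Only a secondary objective is affected, and no primary endpoint or dose criterion.

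**What to change.** In Section 9.4, or in the PK analysis plan to which SAP Section 6.3 defers:

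1. Restrict the HIV markers tested as PK covariates to pre-dose baseline RNA and CD4.
2. State that the exposure in the linked PKPD model comes from a PK model without post-baseline response markers, or is the non-compartmental AUC12h, and that response enters only as the dependent variable.
3. Report any association of post-baseline response with PK under objective 2.25 separately, as descriptive.
4. Add the adherence measures already collected as a candidate covariate on the sparse samples, since removing the response marker does not remove adherence confounding.
5. Settle on one entry threshold, 3.84 or 6.6.

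The cost is a few sentences of wording and, for item 4, one more candidate covariate. No new data are needed, and objective 2.25 is still met.

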The observed geometric mean ETR AUC_{12h} for the first six children was 2576 ng.h/mL. Two of the six children had an individual AUC_{12h} below 2350 ng.h/mL and had dose increases per protocol (see Section 9.34). Short-term safety and antiviral activity data did not reveal any concerns.

Based on the combined pharmacokinetic data, even though the mini-cohort had passed the applicable criteria at that time of no more than 2 subjects with $AUC_{12h} < 2350$ ng.h/mL, and no safety or efficacy concerns, it was evident that with the 5.2 mg/kg dose, the probability of meeting the necessary criteria for the overall cohort (n=12, geometric mean AUC_{12h} 3618-5879 ng.h/mL) would be very low. Therefore, it was decided to modify the ETR dosing regimen for the cohort, prior to recruiting additional subjects.

[figure not shown]
To determine the most appropriate dosing regimen, a modeling and simulation approach was applied. For this, a population pharmacokinetic model of ETR for the pediatric population was used which is structurally based on a previously developed ETR population pharmacokinetic model in adults, using all rich and sparsely sampled pharmacokinetic data from pediatric subjects (6 to 17 years from studies TMC125-C126 and TMC125-C213 [PIANO]; 2 to 6 years from the first mini-cohort in P1090 [all doses, all samples]). The model consists of a sequential zero- and first-order absorption process with a lag-time and one-compartment disposition, includes a covariate effect of body weight on volume of distribution (Vc/F) and clearance (CL/F), and an allometric exponent for CL/F and Vc/F of 0.75 and 1.00, respectively.

Standard graphical and numerical evaluation techniques (goodness-of-fit plots, including observed versus population and individual predicted ETR plasma concentrations, and conditional weighted residuals versus time since first dose and time since last dose), showed that the model fit the data with high precision and minimal bias. So far, no impact of age on the ETR CL/F has been observed. It was also shown specifically for the 6 subjects already enrolled in P1090 that their ETR pharmacokinetic parameters were well estimated with the model. Therefore, the final model was considered suitable for further simulations to evaluate potential dosing regimens for the pediatric population of interest for P1090.

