Introduction of a maturation function did not show any significant improvement in the model based on the current data. As maturation is known to exist, these results suggest that the available data are insufficient to estimate the effect of age on the PK of ETR. Therefore, additional data in younger patients is needed (Cohorts II and III).

Given the uncertainties around maturation of CYP metabolism in subjects aged <1 year, some additional precautions are taken for Cohort III:

- 6 months to < 1 year: the dose (in mg/kg) is reduced by 25% compared to what the model suggests to adjust for possible ongoing maturation of enzymatic metabolism (30)
- 2 months to < 6 months: subjects in this age group will only be included once there are available data on subjects aged 6 months to 1 year

Safety of the weight-based dosing in the younger participants is anticipated to be acceptable based on the safety data collected so far among subjects in Cohorts I and II. The latter was opened 30 October 2015 and, based on input from participating sites in late 2015, the expectation is that there will be at least 2 and likely 6 participants already enrolled in Cohort II by the time of release of Version 5.0. There are adequate safeguards included in the protocol, which include:

- Intensive PK evaluation with individual dose adjustment if needed and continuous safety monitoring on an individual level;
- Close monitoring of PK data and continuous safety monitoring on a cohort level;
- Additional safety monitoring rules for first 6 patients entering cohorts II and III combined.

In conclusion, the added scientific value of the collected data -and the precautions taken to ensure safety and efficacy of the compound in this age group- justifies an early enrollment of Cohort III.

Other Available Data

In a Spanish cohort of five children (5 to 12 years old) and 18 adolescents (13 to 18 years old) of whom 22 had a history of NNRTI-based CART failure with proven genotypic NNRTI resistance mutations, salvage regimens including ETR at 5.2 mg/kg BID (for children) and 200 mg BID (for adolescents) and (in 21 of the patients) OBR with at least 2 active agents, 87% achieved HIV-1 RNA< 400 copies/mL and 78% achieved HIV-1 RNA< 50 copies/mL by 8 months. Mild (3 adolescents) or moderate (2 adolescents) rash was observed only in adolescents but not in children, and therapy was otherwise well tolerated (31).

Table 5. Adverse Events Summary (Adult Studies Phase IIb /III Pooled Analysis)

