8.4 Sample Size and Accrual

8.41 Pharmacokinetics

Sample size for this study was estimated using a pharmacokinetic modeling and simulation approach. Details of this approach are provided in Supplemental Document I. Briefly, the objectives of this approach were to ensure that 1) the mean value of ETR apparent oral clearance (CL/F) has a standard error <20% on 80% of occasions and 2) that the 95% confidence interval for CL/F is 60 to 140% or 60 to 166.6% of the point estimate of the geometric mean on 80% of occasions in each of the above age groups. A third approach was developed and consisted of simulation-estimation platform incorporating data from previous trials. It was used to determine the number of pediatric subjects required across the age range of 2 months to <6 years to ensure the median estimate for CL/F for a typical subject within each age group has a reported standard deviation <20%. Based on a pharmacokinetic model adapted for pediatric maturation and incorporating prior data, a minimum of 12 subjects in each age group is deemed sufficient to provide pharmacokinetic data for pediatric subjects treated with ETR.

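### Section 9.4's stepwise search has low power to separate a moderate maturation effect from body weight, and it is not the model that Section 8.41 uses to support 12 children per cohort

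*Protocol*

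**What the plan says.** Protocol Section 9.4 builds new base models and then screens covariates, with age and weight on the same list as sex, race, background regimen and response markers: "The influence of each covariate on the PK characteristics of ETR will be tested sequentially". It names neither an allometric exponent nor a maturation function. Earlier data are optional: "P1090 data may be supplemented with other pediatric PK data from previous etravirine studies", and then only if needed for the structural model or parameter precision.

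Its selection rule is given twice. One sentence begins "For forward addition and backward elimination a decrease in objective function value by 3.84" (p = 0.05), gives 6.64 (p = 0.01) for elimination, and ends "respectively, would advocate sufficiently influential covariates". The next paragraph says "A difference in objective function of greater than 6.6 is considered significant" when one parameter is added.

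Other sections describe a different model. Section 1.32 reports a pooled pediatric model with weight on clearance and volume and "an allometric exponent for CL/F and Vc/F of 0.75 and 1.00, respectively". It says that a maturation term did not improve that model, that maturation nevertheless exists, and that "these results suggest that the available data are insufficient to estimate the effect of age on the PK of ETR"; data from Cohorts II and III are needed for that reason. Section 3.5.3 makes enrolment below 6 months depend on having enough data to judge how age affects PK. Section 8.41 justifies the cohort size this way: "Based on a pharmacokinetic model adapted for pediatric maturation and incorporating prior data, a minimum of 12 subjects" in each age group. SAP Section 6.3 leaves PK to the pharmacologist and adds no method.

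**The concern.** Among children from 2 months to 6 years, weight and age rise together. If clearance is immature in infancy, a free weight slope can steepen to imitate that, or an age slope can stand in for weight. A search that admits either term on its own merits will then usually keep one and drop the other, and which one it keeps says little about maturation.

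What is at stake is interpretation. The infant cohorts were opened partly to learn the effect of age. A selection result from this search, in either direction, would not settle it. The planned analysis also drops the two features, a maturation term and prior data, on which 8.41 rests its 12 children per group.

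**Working it through.** **Inputs from the documents.** Thresholds 3.84, 6.64 and 6.6 (9.4); 12 children per cohort (8.41); weight exponent 0.75 on CL/F (1.32); one sparse sample at each of weeks 4, 8, 12, 24 and 48 after the Day 14 profile (9.36); 94 earlier children, 74 from PIANO and 20 from TMC125-C126 Stage II (1.32). The documents give no maturation effect. The only figure available as a proxy is the 25% precautionary mg/kg reduction at 6 to <12 months (1.32).

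**Assumptions.** Weights about 5.3, 9.3, 11.8 and 20 kg at 2, 12, 24 and 72 months with 12% spread; 6 infants under 6 months; between-child log-SD 0.40-0.65; occasion error 0.4-0.6 on the log scale. Two document figures support the log-SD range:
- PIANO age 6 to <12: √ln(1 + (2845/5260)²) = 0.51.
- The virtual trials in 1.32 (n = 12; 80% within 80-130%, 96% within 60-150%) imply about 0.58: a standard error of 0.58/√12 = 0.167, centred about 11% above the adult value, reproduces both.

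**1. Stated thresholds.** Chi-square with 1 df is 3.841 at 0.05 and 6.635 at 0.01, so the stated p-values are right. The 6.6 rule has p = 0.0102, so the two criteria for adding a covariate differ about fivefold in p.

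**2. What 12 per cohort buys.** The 8.41 target is a CL/F standard error below 20% on 80% of occasions. This needs s/√12 < 0.20, so s < 0.693. At a true log-SD of 0.60, P(χ²₁₁ < 11 × 0.48/0.36 = 14.67) = 0.80. The target is met, but it concerns precision within an age group, not separation of age from weight.

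**3. Collinearity.** The growth curve gives r of about 0.93-0.94. With one value per child, the variance of the age slope after weight is multiplied by 1/(1 − r²), which is 7.4 to 8.6. The 36 children carry as much information on age given weight as 36(1 − r²), or 4.2 to 4.9, would if the two were unrelated.

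**4. Power of the 9.4 search.** Simulation of log CL/F = a + b·log(weight) + log m(age) + child effect + occasion error, true b = 0.75, fitted by generalised least squares with known variances, 250-400 runs per scenario (Monte Carlo SE up to about 3 points). The 25% effect was either a smooth curve (clearance fraction 0.41, 0.63, 0.75, 0.83 and 0.95 at 2, 6, 9, 12 and 24 months) or a flat step below 1 year. Power to add age after weight, P1090 data only:

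| Scenario | at 3.84 | at 6.64 |
|---|---|---|
| 25%, Day 14 only | 7-29% | 1-12% |
| 25%, all visits, occasion error 0.4 | 18-49% | 5-26% |
| 40% at 9 months, Day 14 only | not tabulated | 13-31% |
| 40% at 9 months, all visits | not tabulated | 43-72% |
| No maturation | 4-6% | 0-1% |

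Pooling the 94 earlier children with weight still free gives, for the 25% effect at 6.64, 4-37% (Day 14) and 19-74% (all visits, occasion error 0.4).

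**5. What the search keeps.** Both terms survived in 0-2% of P1090-only runs. Under smooth maturation, the weight-only exponent drifted from 0.75 to about 1.1-1.5 across the settings tried. With the 25% effect, all visits and occasion error 0.6, the final model was weight alone in 30-47% of runs and age alone in 53-70%. With no maturation, on Day 14 data at log-SD 0.5, it was still age alone in 21%.

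**6. After the change.** With weight fixed at 0.75 and one maturation term, P1090 data only, 25% effect, power at 6.64 is 11-71% (Day 14), 72-94% (all visits, occasion error 0.4) and 37-82% (occasion error 0.6; log-SD 0.50 and 0.65 only). In one common setting (clearance proportional to age/(age + 4 months), log-SD 0.5, one value per child, threshold 6.64), power is about 7% as written, about 25% with pooling alone, about 50% with fixed weight and a maturation term, and about 80% with both.

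A hand check shows the remaining limit. Compare Cohort III (12) with the other 24, weight effect exactly known, flat 25% effect, log-SD 0.5: −ln 0.75 = 0.288; SE = 0.5 × √(1/12 + 1/24) = 0.177; ratio 1.63. Power is 37% at p = 0.05 and 17% at p = 0.01.

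**The case against.** Section 9.4 does not set doses. Sections 3.4 and 9.351 accept a dose on each cohort's own geometric mean AUC12h, obtained by non-compartmental analysis, and Cohort III has its own dosing table. Where a starting dose is revised, 9.351 and Appendix III already require modelling on all available PK data. A reader might infer that the search would misstate infant dosing; the documents do not support that. Attribution is also not prediction. In a simulation with smooth maturation, a weight-only fit missed clearance by only 3-4% at 9 months, 6-10% at 18 months and 2-3% at 48 months, although it was 16-32% too high at 3 months.

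A reader might also infer that the analysis has almost no power, or that it will probably report no age effect. The first ignores the week 4-48 samples and the permitted pooling: a 40% effect with all visits reaches 43-72%. The second ignores that the search often keeps age and drops weight.

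Further points stand. Poor precision is itself a stated ground for pooling. Covariate relationships are a secondary objective, to be explored. Section 1.32 does not say that its exponents were fixed. The comparison in step 6 favours the change, because the fitted maturation shape is the one that generated the data. None of this supplies a prespecified way to estimate maturation, which is the gap.

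**Conclusion.** The point holds as a matter of interpretation and consistency. As written, 9.4 has low power to separate a moderate maturation effect from weight: 1-26% at the retention threshold for a 25% effect on P1090 data alone. It almost never keeps both terms, so neither a weight-only nor an age-only final model would say much about maturation. It is also not the model with maturation and prior data behind the 12 per group in 8.41. The free weight slope is the larger cause, and optional pooling the smaller. Dose acceptance is untouched.

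The figures rest on an assumed growth curve, maturation shape, variability and occasion error, on a proxy effect size, and on a regression approximation rather than NONMEM. The sponsor's own sample-size simulation is in Supplemental Document I, which was not available to rerun. The change is a cheap improvement, not a correction of an invalid analysis.

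**What to change.** Amend Section 9.4 as follows:

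1. Start from the Section 1.32 model, with weight on CL/F and Vc/F at exponents 0.75 and 1.00. Make freely estimated exponents a sensitivity analysis.
2. Replace the optional supplementation with a statement that P1090 data will be pooled with TMC125-C126 and TMC125-C213.
3. Fit one prespecified maturation function of age on CL/F before any other covariate. Report its estimate and confidence interval whether or not it passes the threshold.
4. Report CL/F precision by cohort against the 20% in 8.41.
5. Reconcile the 3.84 forward-addition criterion with the 6.6 criterion for adding a parameter, and state which applies.

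The cost is analysis-plan text only, since the model and the earlier data already exist. The main model then assumes that the allometric exponents hold below 6 years, which the sensitivity analysis checks. Power stays limited for a small effect, which is why the interval matters more than the selection result.
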